## PFIZER GENERAL BUSINESS

- Variable: Response based on improvement of ≥75% from baseline SCORAD total score at Week 12; participants who discontinued intervention for any reason or required a rescue medication are considered as non-responders;
- Intercurrent event: The intercurrent event "intervention discontinuation for any reason" is addressed in the variable definition;
- Population-level summary: SCORAD75 response rate with 95% CI, in each treatment arm.

The secondary estimand 4 is defined according to the secondary objective and in alignment with the secondary endpoint change from baseline in POEM scores. It includes the following 4 attributes:

- Population: Patients aged 12 years and older with moderate to severe AD, as defined by the inclusion and exclusion criteria, and who are randomized;
- Variable: Change from baseline in POEM scores at Week 12 and at all scheduled time points; data after treatment discontinuation or use of rescue medication at any time during the treatment period will be censored;
- Intercurrent event: The intercurrent event "intervention discontinuation for any reason" is addressed in the variable definition;
- Population-level summary: Mean and standard deviation (SD), in each treatment arm.

The secondary estimand 5 is defined according to the secondary objective and in alignment with the secondary endpoint change from baseline in ADCT scores. It includes the following 4 attributes:

- Population: Patients aged 12 years and older with moderate to severe AD, as defined by the inclusion and exclusion criteria, and who are randomized;
- Variable: Change from baseline in ADCT scores at Week 12 and at all scheduled time points; data after treatment discontinuation or use of rescue medication at any time during the treatment period will be censored;
- Intercurrent event: The intercurrent event "intervention discontinuation for any reason" is addressed in the variable definition;
- Population-level summary: Mean and SD, in each treatment arm.

## PFIZER GENERAL BUSINESS

## 2.1.3. Additional Estimand(s)

The primary substudy estimand is the incidence of bone safety findings in knee MRI after 1 year of being exposed to abrocitinib in adolescent participants 12 to <18 years of age, regardless of dosing compliance or treatment discontinuation. This estimand is defined according to the primary substudy objective and is in alignment with the primary substudy endpoint. It includes the following 4 attributes:

- Population: Patients aged 12 to <18 years with moderate to severe AD, as defined by the substudy inclusion and exclusion criteria;
- Variable: Binary indicator of whether the participant had bone safety findings in knee MRI 1 year after randomization;
- Intercurrent event(s): Dosing compliance or treatment discontinuation is not considered for analysis. All data collected (including data after discontinuation of treatment) are included.
- Population-level summary: Incidence rate of bone safety findings, defined as the number of participants with bone safety findings in knee MRI 1 year after randomization divided by the number of participants that received treatment during the substudy, in each treatment arm.

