10.10.8.1. Bone Safety Findings Identified in Central Evaluation of Knee MRI Images

All bone safety findings will be recorded in the CRF as either medical history or treatment emergent adverse events, as determined by the Investigator.

If any bone safety finding(s) are determined to be present in the central evaluation of the postdose knee MRI images, then the adjudication committee will adjudicate the diagnosis as per the adjudication charter.. The adjudication committee may suggest further follow up or investigation for Investigator consideration. The Investigator will receive a report of the MRI central read and the adjudication outcome, and will determine if any further follow-up or investigation is required.

The Investigator will ensure the recording of any AEs as described in the Adverse Event Reporting section (Section 8.3 and Section 10.10.9), or medical history, if relevant.

If any potential bone safety findings, as per the image review charter, are determined to be present in the MRI central read report, then these findings are to be reported to Pfizer Safety as an important medical event on the CT SAE form within 24 hours of awareness of the event. These potential bone related safety findings are to initially be detailed as potentially related to study intervention under study. If subsequently determined (e.g. following further history, examination, investigation, adjudication) that the finding is unrelated to study intervention, then this must be updated by submitting a follow up CT SAE form within 24 hours of awareness.

Incidental/Unrelated Findings:

An incidental finding is one unknown to the participant and has potential health or reproductive importance, which is discovered unexpectedly in the course of a research study, but is unrelated to the purpose and beyond the aims of the study.

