#### PFIZER GENERAL BUSINESS

# Figure 1. Study Design (Main Study)

# **3. ENDPOINTS AND BASELINE VARIABLES: DEFINITIONS AND CONVENTIONS**

## 3.1. Primary Endpoint(s)

The primary endpoint is the incidence of AEs/SAEs, defined as the number of participants with treatment emergent adverse events, divided by the number of participants in the Safety Population (Section 4).

An adverse event will be considered treatment emergent relative to a given treatment if:

• The event starts on or after the first dose of study drug, but before the last dose plus the lag time of 28 days. The algorithm will not consider any events that started prior to the first dose date. If an AE starts on the same day as the first dose date, it will be considered treatment emergent.

or

• The event was seen prior to the start of study drug but increased in severity during the effective duration of treatment.

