#### PFIZER GENERAL BUSINESS

## 3.5.4. Electrocardiograms

Electrocardiograms (ECG) parameters to be summarized include heart rate, PR, QT, QTcF and QRS.

Population	Description
Enrolled	All participants who sign the informed consent document.
Full analysis set (FAS)	All participants randomly assigned to study intervention and who take at least 1 dose of study intervention. Participants will be analyzed according to the treatment arm they are randomized to.
Safety	All participants randomly assigned to study intervention and who take at least 1 dose of study intervention. Participants will be analyzed according to the treatment they actually received.
Substudy analysis set (SAS)	All participants who entered the substudy and who take at least 1 dose of study intervention during the substudy.

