## 5.2. General Methods

## 5.2.1. Analyses for Binary Endpoints

Binary endpoints (response based on IGA, EASI-75 and SCORAD75 and incidence of bone safety findings) will be presented using proportions together with the 95% confidence

PFIZER GENERAL BUSINESS

interval calculated using the normal approximation (or the Clopper-Pearson exact method when the estimated proportion is 0 or 1). Incidence of adverse events will be presented using frequency counts and percentages.

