## 6.3. Other Endpoint(s)

#### 6.3.1. Incidence of bone safety findings in knee MRI

- Estimand strategy: Treatment policy (Section 2.1.3).
- Analysis set: SAS (Section 4).
- Analysis methodology: Descriptive statistics and 95% CIs.
- Intercurrent events and missing data: All data collected will be analyzed regardless of dosing compliance or treatment discontinuation; missing values will not be imputed.

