## PFIZER GENERAL BUSINESS

• The incidence rate of bone safety findings in knee MRI, along with the 95% CI will be estimated for baseline and End of Treatment (EOT) in the substudy, for each treatment arm. In addition, the types of bone safety findings will be summarized.

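### SAP 2.1.3 keeps treated adolescents without a post-dose knee MRI in the denominator of the substudy's primary bone-finding rate, which lowers the rate and its upper confidence limit

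*SAP*

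**What the plan says.** **Rate.** SAP 2.1.3 defines the variable as "Binary indicator of whether the participant had bone safety findings in knee MRI 1 year after randomization". The summary is the number with such a finding "divided by the number of participants that received treatment during the substudy, in each treatment arm".

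**Analysis set.** SAP Section 4 defines the substudy analysis set (SAS) as "All participants who entered the substudy and who take at least 1 dose of study intervention during the substudy". No MRI is required.

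**Missing scans.** SAP 6.3.1: "All data collected will be analyzed regardless of dosing compliance or treatment discontinuation; missing values will not be imputed". SAP 5.2.1 presents the endpoint as a proportion with a normal-approximation 95% CI, or Clopper-Pearson when the estimate is 0 or 1.

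**Timing.** The protocol's substudy schedule (10.10.2) puts the end-of-treatment (EOT) visit at Day 1 + 365 days, ±14. Protocol 10.10.7.2 has the MRI arranged within about 1 month of that visit. Protocol 10.10.7.3 provides a catch-up MRI, before the follow-up visit, if none was done. SAP Appendix 2.1 assigns MRI to Days 353 to 380 or early termination. Its next row, Days 381 to 408, is for HSS Pedi-FABS only.

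**Baseline.** SAP 6.3.1 says the same incidence rate "along with the 95% CI will be estimated for baseline and End of Treatment (EOT) in the substudy". Protocol 10.10.8.1 adds: "All bone safety findings will be recorded in the CRF as either medical history or treatment emergent adverse events". For adverse events, SAP 3.1 does have a worsening rule: "The event was seen prior to the start of study drug but increased in severity during the effective duration of treatment". No counterpart is given for MRI findings.

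**The concern.** The rate and its confidence limits in each arm are the substudy's main result, and there is no untreated group to compare with. When few or no findings occur, the upper limit is the number that readers will use. A denominator that includes people who were never examined makes that limit look tighter than the imaging supports.

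Two further points bear on the same number. A window narrower than the protocol's scan timing can leave a valid scan without an analysis row. And if findings already present at baseline count again at EOT, the figure labelled incidence is really a prevalence at one year.

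**Working it through.** **Inputs.** The documents give no number of adolescents, no expected finding rate and no MRI completion rate, so every count below is an assumption. The only sample-size figure is the main-study margin of 10% with 100 per arm (Protocol 9.5). It reproduces as 1.96 × √(0.25/100) = 9.8%, but says nothing about the substudy.

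**Step 1: denominator, no findings.** The exact upper 95% limit for 0/n is 1 − 0.025^(1/n).

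| Treated | Upper limit, all treated (SAP 2.1.3) | Upper limit, scanned only |
|---|---|---|
| 10 | 30.8% | 33.6% (9 scanned); 36.9% (8) |
| 25 | 13.7% | 14.2% (24); 15.4% (22); 16.8% (20) |
| 50 | 7.1% | 7.4% (48); 7.9% (45); 8.8% (40) |

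**Step 2: denominator, one finding.** The normal-approximation upper limit is p + 1.96√(p(1−p)/n).
- 1/25: 4.0%, upper limit 11.7%
- 1/24: 4.2%, upper limit 12.2%
- 1/20: 5.0%, upper limit 14.6%

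**Step 3: bounds on all treated.** With x findings among s scanned of N treated, the rate lies between x/N and (x + N − s)/N. For x = 1 and N = 25, this is 4.0% to 2/25 = 8.0% with one unscanned, and 4.0% to 6/25 = 24.0% with five. The lower bound is the number that 2.1.3 reports.

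**Step 4: window.** Day 1 + 365 = Day 366, and ±14 gives visits on Days 352 to 380. A scan on Day 352 is one day before the SAP window. A scan 15 or more days after a Day 366 visit, or one or more days after a Day 380 visit, falls on Day 381 or later. In a 1-year completer neither has an MRI row. The catch-up MRI can fall there too.

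**Step 5: numerator (conditional).** Let r be the share scanned, b the share with a persisting baseline finding, and q the risk of a new finding in the rest, with r independent of b and q. The expected SAP proportion is r × (b + (1 − b)q).
- r = 0.8, b = 0, q = 10%: 8.0%, below the true new-finding risk
- r = 0.8, b = 10%, q = 0: 8.0%, although nothing is new

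Separate baseline and EOT rates do not resolve this. If the same 20 are scanned twice, with 2 findings at baseline and 3 at EOT, the number with a new finding can be anything from 3 − 2 = 1 to 3, that is 5% to 15% of those scanned. With 25 treated the SAP would report 3/25 = 12.0%.

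**Step 6: participants who turn 18.** Footnote c of Protocol 10.10.2 gives those who turn 18 during the main study a baseline MRI only. Protocol 10.10.7.2 plans a termination visit with MRI on turning 18, and 10.10.7.4 can be read either way. If ages are uniform from 12 to under 18, the group is 84/365.25/6 = 3.8% of adolescents.

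**The case against.** **Missing data.** No sentence says that an unscanned participant is finding-free, and coding one as such would itself be imputation, which 6.3.1 rules out. A reader could take 6.3.1 as a complete-case rule. That stands as an ambiguity, but a complete-case rate contradicts the denominator in 2.1.3, so one of the two must be changed. SAP 5.2.3 shows missing values as a separate category for categorical endpoints. If it applied here, the number unscanned would be visible, but the denominator would still be all treated.

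**Few unscanned.** The protocol plans early-termination MRIs (10.10.4, 10.10.7.2) and a catch-up scan, and one unscanned in 25 moves the upper limit by only half a point. This stands. It is also not fully clear that treatment in the substudy counts from Day 1. The substudy schedule places its baseline and first dispensing there, but 10.10.6 can be read as starting after Week 12. The later start would reduce the number unscanned without changing the rule.

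**Window.** Because 6.3.1 analyses all data collected, it is not established that an out-of-window scan would be discarded. What stands is that the SAP assigns it nowhere.

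**Numerator.** What counts as a finding is set by the image-review and adjudication charters, which are not supplied. The substudy requires a knee without a history of significant trauma or abnormality, which makes baseline findings less likely, so the 10% used above is illustrative only. The protocol endpoint is a proportion at 1 year, not a risk of new findings. The adverse event analysis on the SAS (SAP Section 5) will show what investigators record as treatment emergent. All of this stands, and it is why the numerator point is secondary.

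**Conclusion.** The denominator point holds on the SAP's own formula: each treated adolescent without a post-dose MRI lowers the rate and its upper limit. With zero findings and 25 treated (assumed), the upper limit is 13.7%, against 14.2% if 24 are scanned and 16.8% if 20 are. The true shift is unknown and may be small. The window mismatch also holds as a matter of text.

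A reader might go further and infer that the reported rate is known to be a prevalence, or that new findings will be hidden. The documents do not support either. The charters may already restrict findings to new or worsened ones, and potential findings on the central read must be reported to the sponsor's safety group within 24 hours. The supportable statement is conditional: unless the charters make that restriction, the EOT figure is a prevalence. Since the two effects act in opposite directions, the SAP alone does not show which way the figure departs from the risk of a new finding.

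**What to change.** (a) In SAP 2.1.3 and 6.3.1, use as denominator the SAS participants with at least one readable post-dose MRI. Report the number unscanned by arm and reason, and give a best/worst-case range on all treated.

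(b) In Appendix 2.1, widen the MRI window to cover every post-dose scan that the protocol permits, including Day 352 and the catch-up MRI. Count a participant as having the event if any post-dose MRI shows an adjudicated finding, so that neither a repeat scan nor the closest-to-target rule removes one. Correct the sentence limiting windows to efficacy variables, since the table itself lists MRI.

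(c) Label the any-finding rates at baseline and EOT as prevalence. Add the number with a finding new or worsened against their own baseline MRI, or cross-refer to the charter if it already defines this. List separately anyone without a readable baseline, so that a post-dose finding is not lost.

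(d) Reconcile footnote c of Protocol 10.10.2 with 10.10.7.2 and 10.10.7.4 on participants who turn 18 during the main study, and state whether they are in the SAS.

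Cost: slightly wider intervals and a little more programming, on scans already planned. Item (d) needs a protocol clarification. The adjudication charter may need a line giving the committee the baseline images if it does not have them.

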## 2.2. Study Design

This is a randomized, open-label, parallel-group study to evaluate the safety and efficacy of abrocitinib 100 mg QD and 200 mg QD tablets in participants aged 12 years and older with moderate to severe AD in India. There is a planned treatment duration of 12 weeks, with 4 weeks of off-treatment safety follow up thereafter. Study participants will be screened within 28 days prior to the first dose of investigational product to confirm that they meet the eligibility criteria for the study.

This study protocol also includes a substudy evaluating whether abrocitinib has any potential effects on adolescent bone with regard to bone safety findings in knee MRI. Adolescent participants (12 to < 18 years of age) will continue to receive investigational product until 1 year after randomization into the main study.

#### PFIZER GENERAL BUSINESS

# Figure 1. Study Design (Main Study)

# **3. ENDPOINTS AND BASELINE VARIABLES: DEFINITIONS AND CONVENTIONS**

## 3.1. Primary Endpoint(s)

The primary endpoint is the incidence of AEs/SAEs, defined as the number of participants with treatment emergent adverse events, divided by the number of participants in the Safety Population (Section 4).

An adverse event will be considered treatment emergent relative to a given treatment if:

• The event starts on or after the first dose of study drug, but before the last dose plus the lag time of 28 days. The algorithm will not consider any events that started prior to the first dose date. If an AE starts on the same day as the first dose date, it will be considered treatment emergent.

or

• The event was seen prior to the start of study drug but increased in severity during the effective duration of treatment.

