9.1. Statistical Hypotheses

9.1.1. Estimands

9.1.1.1. Primary Estimand

The primary estimand is defined by the following attributes:

Population: Patients aged 12 years and older with moderate to severe AD.

Variable: Binary indicator of whether any AE/SAE occurred at least once.

Treatment condition: The randomized intervention regardless of intercurrent events.

The intercurrent events "intervention discontinuation for any reason" and "intervention compliance" are both addressed by the treatment condition of interest.

Population-level summary: Incidence rate of AEs/SAEs, defined as the number of participants with AEs/SAEs from the time of first dose to Week 16 divided by the number of participants, in each treatment arm.

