9.3.2. Primary Endpoint Analysis

Analysis of the incidence of AEs and SAEs will be performed on the FAS. Participants will be analyzed according to the treatment they actually received. The number and percentage of treatment-emergent AEs will be summarized according to type, frequency, severity, seriousness and relationship to abrocitinib in each treatment arm. In addition, withdrawals from active treatment due to AEs and serious infections, defined as any infection (viral, bacterial, and fungal) requiring hospitalization or parenteral antimicrobials or meets other criteria that require it to be classified as a serious adverse event, will be summarized descriptively.

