# Table 1.Summary of Changes

#### PFIZER GENERAL BUSINESS

# **2. INTRODUCTION**

This statistical analysis plan (SAP) provides the detailed methodology for summary and statistical analyses of the data collected in Study B7451094. This document may modify the plans outlined in the protocol; however, any major modifications of the primary endpoint definition or its analysis will also be reflected in a protocol amendment.

Objectives	Endpoints	Estimands
Primary:	Primary:	Primary:
• To evaluate the safety of abrocitinib in participants aged 12 years and older with moderate to severe Atopic Dermatitis (AD)	• Incidence of adverse events (AEs) and serious adverse events (SAEs)	• The primary estimand for safety is the incidence of AEs and SAEs in participants aged 12 years and older with moderate to severe AD, from the time of first dose to Week 16, regardless of dosing compliance or treatment discontinuation.
Secondary:	Secondary:	Secondary:
• To assess the efficacy of abrocitinib in participants aged 12 years and older with moderate to severe AD	
 
Response based on Investigator's Global Assessment (IGA) score of clear (0) or almost clear (1) and greater than or equal to 2 points improvement from baseline at Week 12
 
Response based on achieving ≥75% improvement from baseline in the Eczema Area and Severity Index total score (EASI-75) at Week 12
 
Response based on ≥75% improvement in Scoring Atopic Dermatitis total score (SCORAD75) at week 12
 
	• The secondary estimand is the treatment effect of abrocitinib on participants aged 12 years and older with moderate to severe AD, based on IGA response, EASI-75 response and SCORAD75 response from baseline to Week 12, considering patients who discontinued treatment as non-responders and based on outcome measures of POEM and ADCT from baseline to Week 12 and at all scheduled time points. Data collected after treatment discontinuation is excluded.

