# 2.1.1. Primary Estimand(s)

The primary estimand is the incidence of AE/SAE regardless of whether an intercurrent event occurs. The estimand is defined according to the primary objective and is in alignment with the primary endpoint. It includes the following 4 attributes:

- Population: Patients aged 12 years and older with moderate to severe AD, as defined by the inclusion and exclusion criteria, and who are randomized;
- Variable: Binary indicator of whether any AE/SAE occurred at least once;
- Intercurrent event(s): Dosing compliance or treatment discontinuation is not considered for analysis. All data collected (including data after discontinuation of treatment) are included.
- Population-level summary: Incidence rate of AEs/SAEs, defined as the number of participants with AEs/SAEs from the time of first dose to Week 16 divided by the number of participants, in each treatment arm.

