## 6. ANALYSES AND SUMMARIES

## **6.1.** Primary Endpoint(s)

## 6.1.1. Incidence of AEs/SAEs

- Estimand strategy: Treatment policy (Section 2.1.1).
- Analysis set: Safety (Section 4).
- Analysis methodology: Descriptive statistics.
- Intercurrent events and missing data: All adverse event data collected will be analyzed regardless of dosing compliance or treatment discontinuation; missing values will not be imputed.
- The number and proportion of participants who had treatment emergent adverse events will be presented for each treatment arm. Treatment emergent adverse events will be summarized according to type, frequency, severity, seriousness and relationship to abrocitinib in each treatment arm.

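### The SAP's working definition of the primary AE/SAE incidence has no Week 16 limit, so adolescents' later events can enter a figure defined as first dose to Week 16

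*SAP*

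**What the plan says.** The estimand has a fixed window. The objectives table in SAP 2.1 sets the primary incidence "from the time of first dose to Week 16, regardless of dosing compliance or treatment discontinuation". SAP 2.1.1 gives the summary measure as "participants with AEs/SAEs from the time of first dose to Week 16 divided by the number of participants", and protocol 9.1.1.1 matches it.

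The endpoint definition has a different window. SAP 3.1 counts participants with treatment-emergent events over the Safety population. An event qualifies by onset: "The event starts on or after the first dose of study drug, but before the last dose plus the lag time of 28 days". It also qualifies by worsening: "The event was seen prior to the start of study drug but increased in severity during the effective duration of treatment". Neither limb mentions Week 16.

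The analysis follows the endpoint definition. SAP 6.1.1 states: "The number and proportion of participants who had treatment emergent adverse events will be presented for each treatment arm". It and Appendix 1 include all AE data collected. Protocol 9.3.2 also summarises treatment-emergent AEs but does not define their window.

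Participants aged 12 to under 18 "will continue to receive investigational product until 1 year after randomization into the main study" (SAP 2.2); protocol 10.10.6 adds that dosing ends if they turn 18. All of them enter the substudy (protocol 10.10.4), and all who are randomised and dosed are in the Safety population (SAP 4).

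**The concern.** The two definitions agree only for someone who takes about 12 weeks of drug. An adolescent who stays on treatment keeps the SAP 3.1 window open long after Week 16. A programmer working from 3.1, 6.1.1 and Appendix 1 would apply no cut at Week 16.

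The main-study incidence would then mix roughly 16 weeks of observation in adults with up to 56 weeks in adolescents. It would depend on how many adolescents an arm contains and how early they enrolled, neither of which belongs to the estimand. The study is descriptive (SAP 5.1), so no test or error rate is at stake. What is at stake is the reported incidence per arm for the only primary endpoint.

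**Working it through.** **The plan's own precision figure.** Protocol 9.5 states a maximum margin of error of 10% with 100 participants per arm. The 95% normal-approximation half-width at p = 0.5 is 1.96 × √(0.25/100) = 0.098, or 9.8 points. The figure reproduces and is a useful yardstick below.

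**Windows in days.**
- Estimand: Week 16 is nominally Day 16 × 7 + 1 = 113.
- Adult completers: the Week 12 visit is Day 85 ± 3 (protocol 1.3). Last dose on Day 82 / 85 / 88 plus 28 gives Day 110 / 113 / 116. Because the rule says before that day, events count through Day 109 / 112 / 115.
- End-of-study visit: 28 days after Day 82 to 88, ± 3, is Day 107 to 119.
- One-year adolescents: end of treatment is Day 1 + 365 = 366 (protocol 10.10.2), and 366 + 28 = 394. That is 281 days beyond Day 113 and 394/113 = 3.5 times as long.

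**Illustrative size.** The documents do not give the adolescent share, accrual time or AE incidence, so all inputs here are assumptions:
- accrual is uniform over A weeks, and the main-study data are cut at Week 16 of the last participant;
- an adolescent enrolled at week u is observed for w = min(56, A + 16 − u) weeks, where 56 = 52 weeks of dosing + 4;
- incidence by week w is 1 − (1 − p16)^((w/16)^k), with k = 1 for a constant hazard and k = 0.5 for early clustering;
- shift in the arm = f × (mean adolescent incidence − reference), where f is the adolescent share.

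With p16 = 0.50 the reference is 0.500 at Day 113. At Day 119 (17 weeks) it is 0.521 (k = 1) or 0.511 (k = 0.5). For f = 0.2, each cell gives k = 1 / k = 0.5:

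| Accrual (weeks) | Mean w (weeks) | Adolescent incidence | Shift vs Day 113 (points) | Shift vs Day 119 (points) |
|---|---|---|---|---|
| 13 | 22.5 | 0.618 / 0.558 | +2.4 / +1.2 | +1.9 / +1.0 |
| 26 | 29.0 | 0.700 / 0.600 | +4.0 / +2.0 | +3.6 / +1.8 |
| 52 | 40.6 | 0.797 / 0.657 | +5.9 / +3.1 | +5.5 / +2.9 |

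Example: 0.2 × (0.797 − 0.521) = 0.055.

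**Sensitivity (Day 119 reference, 26 to 52 weeks' accrual).**
- Shares of 10% to 30%: +1.8 to +8.3 (k = 1), +0.9 to +4.4 (k = 0.5).
- p16 of 30% or 70%, share 20%: +2.9 to +5.2 (k = 1), +1.4 to +2.6 (k = 0.5).
- Ages uniform over 12 to under 18 with dosing ending at 18, share 20%, k = 1: +3.3 / +5.1.
- SAE incidence of 2%, share 20%: +0.1 to +0.6.

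**Ceiling.** If every adolescent had full follow-up to Day 394 under a constant hazard, a 20% share would add 8.2 points at 30% incidence and 7.2 at 60%. A main report issued before all adolescents reach one year would fall short of this.

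**The case against.** The best defence is that the limit is already stated. SAP 6.1.1 cites 2.1.1, whose summary measure ends at Week 16, so 3.1 could be read as only classifying events as treatment-emergent within that window. Other passages point to a 12-week main dataset. SAP 5 reports main study and substudy separately and repeats 6.1 on the substudy set, protocol 10.10.2 calls Week 12 the main-study end of treatment, protocol 6.1 describes 12-week arms, and the exposure categories in SAP 6.5.3 stop at 10 weeks or more.

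These passages make a main-period table a plausible intention, but none sets an AE cut. SAP 6.1.1 cites 2.1.1 for the estimand strategy and then tabulates treatment-emergent events, which 3.1 defines as the primary endpoint itself. SAP 5 fixes when each report is issued, not which events count; by main-study completion, early-enrolled adolescents can have months of later events on the database. The visit windows in SAP Appendix 2.1 apply to efficacy variables.

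Three further points stand in part. The magnitude is illustrative, and every accrual-based scenario lies below the 10-point margin of error; still, this is a systematic shift, which a confidence interval does not cover. The upward direction is shown for adolescents only: for early stoppers, 3.1 drops any events collected between last dose + 28 days and Week 16, which works the other way, and no figure can be put on it. The rest of their shorter window comes from protocol follow-up (protocol 1.3, 7.1 and 8.3.1), not from 3.1. Lastly, Appendix 1 and 6.6.1 need matching text as well as 3.1 and 6.1.1.

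**Conclusion.** The concern holds. SAP 3.1 and 6.1.1 do not implement the window in SAP 2.1, SAP 2.1.1 and protocol 9.1.1.1, and nothing elsewhere sets an AE cut for the main table. Adult completers are practically unaffected. Adolescents' events after Week 16 can enter the primary incidence and raise it. At a 20% adolescent share, 50% incidence by Week 16 and 26 to 52 weeks' accrual, the rise is about 2 to 6 points per arm, and under 1 point for SAEs at 2%. It is smaller with faster accrual or fewer adolescents and larger with more. The mismatch in wording is certain; its numerical size is not, because share, accrual, incidence and hazard shape are all assumed. It should be fixed before the main-study analysis.

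**What to change.** In SAP 3.1 and 6.1.1, limit the main-study primary count to events with onset or worsening from first dose to Week 16 for every participant in the Safety population, including events collected after early discontinuation. Carry the same limit into the Appendix 1 row and the main-study AE summaries in 6.6.1.

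Define Week 16 to cover the main-study end-of-study visit: nominal Day 113, up to Day 119. A hard cut at Day 113 would drop Day 114 and 115 events that 3.1 now counts for an adult whose last dose is on Day 88. The six extra days admit a little more on-treatment time in adolescents, about 0.4 points in the 20% constant-hazard example (4.0 − 3.6).

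Apply the limit to the main-study table only, and report adolescents' later events in the substudy report, which already repeats 6.1 on the substudy analysis set. Keep the last dose + 28 days table as supportive, and report how many participants were not followed to Week 16.

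The cost is SAP wording, one onset-date cut-off in programming and one extra count. No protocol change, visit or contact is needed. Two limits remain: early stoppers' shorter follow-up is made visible but not cured, and the cut aligns calendar time rather than exposure, since adolescents are still being dosed in Weeks 12 to 16 while adults are off treatment.
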